Participants will be interviewed by the study team and those with a MAQ score of 1 to 4 will be classified as non-adherent will be invited to participate. The study team member will assess the potential participant's phone ownership, text messaging ability, text messaging willingness, and receptivity to the intervention (and record all this information). The MAQ cut-off was chosen for the study because it has been used in the literature in previous studies,²⁰⁻²² and the cut-off at this value provides a highly sensitive tool for identifying medication non-adherence.^{22,23}

Participants will be randomized into one of two groups: intervention SMS arm or the control arm. If enrolled in the intervention arm, the subjects will be contacted by phone via SMS and phone call. To ensure equal access to participation among women and minorities we will translate all materials and questions to Spanish. The privacy of potential subjects during recruitment will be protected by collecting only necessary identifiers and using a private room during the interview process.

As part of routine care, patients who present to the office with uncontrolled HTN receive instructions from their clinician on medication changes and are advised to return for a nurse visit in 2 weeks and a clinician visit in 3 months. During follow-up, the nurse checks the patient's blood pressure and contacts the clinician for further management if the BP is not controlled. Participants in the SMS arm will receive SMS messages to monitor their blood pressure in addition to this routine care whereas the control arm will only receive the standard provider education and monitoring for controlling blood pressure.

Baseline demographic characteristics of the participants will be collected. Participants will be followed with office (or phone if they no show for their visit) interviews at 2 weeks or 3 months to complete 2 validated scales: the MAQ, and SUS+ free comments

Study intervention participants will be provided with a blood pressure monitor to be used for measurement and extraction of HBPM information. Clinicians will be alerted through an in-basket message in the electronic medical record (Wake One) if the participants report BP outside the threshold range, and the patient will be sent an SMS and prompted to contact their clinic. The threshold range set for SBP is between 90 and 180 mm Hg and between 60 and 110 mm Hg for DBP for one-time measurements. These thresholds are made based on the

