1. Screening: we will track the number of patients screened per month, the number enrolled per month, the proportion that are eligible who enroll.
2. Recruitment: number of participants who refuse to participate in the pilot at the time of recruitment and the reason why. Proportion of vulnerable patients screened but excluded because they did not own a phone with SMS capability.
3. Retention: the proportion of participants who continue to use the myHealth tool per month through three months will be tracked for the intervention.
4. Engagement: 12- SMS rate response of at least one home BP measurement. We will use 44% as our cut off based on an SMS study by Peters and colleagues²⁵.

Finally, we will monitor time needed for assessments and gather feedback on the participant burden.

B-Acceptability

Participants will complete the SUS in person on an I-Pad or over the phone. They will also be offered the opportunity to comment in their questionnaires about their experiences of taking part in the pilot. The SUS yields a single score on a scale of 0–100. A SUS score above a 68 would be considered above average. We will consider acceptable when >70 % of participants score the SUS above 68.²⁶

Secondary measures of interest

Medication adherence (MA) will be measured by administrating the four-item MAQ by the study coordinator during enrollment and at 3 months follow up visit. The MAQ was selected because it has been well-validated to identify adherence in HTN and scores have been shown to correlate well with a range of objective adherence measures.^{11,12}

SBP and DBP change at 3 months. BP will be measured during initial and follow up office visits by nurses or clinicians while patient is seated with automated arm devices according to standard office procedures. We will extract from the electronic medical record, SBP and DBP at enrollment and at 12 weeks follow up. The average change will be calculated and reported in mmHg.

No-show rate at 3 months' follow-up (f/u) clinic visits. If participants fail to come to their f/u visits within 7 days of their scheduled follow-up appointment, they will be considered as "no-shows". Our current clinic no-show rate is 30%, therefore if the study participants no-show rate is less than 30% we will consider our tool a feasible intervention.

Analytical Plan

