Results will be analyzed initially using descriptive statistics. Comparison between groups will be done using chi square tests for proportions, and t-tests for continuous variables. Regression analysis will be performed to identify independent outcome predictors. RedCap will be utilized to collect all patient data. Participant's demographics (including education level), co-morbidities, number of medications, number of blood pressure medications and BP numbers will be extracted from Wake One when available. Level of education will be confirmed verbally with each participant during consent process. Only one participant identifier will appear in the data collection forms.

The full analysis set will include participants who have responded to at least one SMS message post-randomization. Descriptive statistics will be computed for each treatment group; medians and percentiles will be reported for skewed continuous variables. For primary and secondary outcomes, descriptive statistics and 95% confidence intervals will be used to summarize the differences between groups. The secondary outcome of BP and other continuous variables will be assessed with a repeated-measures analysis using a mixed linear model approach. The Wilcoxon rank sum test will be used to compare MA between groups. Hypothesis tests will be 2-sided using the 0.05 significance level. Bonferroni-type adjustments for multiple testing will be implemented to control type I errors. Statistical analysis will be performed using SAS software (SAS Institute, Cary, NC).

Treatment assignment will be determined using blocked randomization

The primary analysis will consist of all subjects who responded with at least one BP measurement

Human Subjects Protection

Subject Recruitment Methods

Subjects will be identified when they come to an office visit and their blood pressure is not well controlled. The PI clinician (internal medicine preceptors or residents) will verbally alert the study coordinator on site of possible participants based on BP >140/90. The study team member will meet the patient in a private room in 7th Janeway, determine eligibility, and signed informed consent will be obtained from each subject. Once enrolled, the subjects will be contacted by phone via SMS and phone call. To ensure equal access to participation among women and minorities we will translate all materials and questions to Spanish. The privacy of

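### Office BP is extracted only at enrolment and 12 weeks, so a participant without a 12-week reading adds nothing after baseline to the mixed model, although a routine 2-week nurse reading could be used

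*Combined protocol and SAP*

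**What the plan says.** The Secondary measures of interest section makes the outcome an office reading: "BP will be measured during initial and follow up office visits by nurses or clinicians while patient is seated with automated arm devices". It then names two time points: "We will extract from the electronic medical record, SBP and DBP at enrollment and at 12 weeks follow up". The Analytical Plan adds: "The secondary outcome of BP and other continuous variables will be assessed with a repeated-measures analysis using a mixed linear model approach". No method for missing data is given.

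The only planning figure for missed visits is in the same outcome section: "Our current clinic no-show rate is 30" per cent. A no-show is defined there by a time limit: "If participants fail to come to their f/u visits within 7 days of their scheduled follow-up appointment". Under Design, no-shows are telephoned about barriers to adherence and the scales may be completed by phone. No replacement BP reading is mentioned.

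Design also describes routine care. Patients with uncontrolled hypertension are "advised to return for a nurse visit in 2 weeks and a clinician visit in 3 months", and "During follow-up, the nurse checks the patient's blood pressure and contacts the clinician for further management if the BP is not controlled". The SMS arm receives its messages on top of this care, and the control arm receives the standard education and monitoring. The 2-week reading should therefore exist in the record for attenders in both arms, but the outcome sentence does not list it.

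**The concern.** A mixed model handles missing outcomes well when it has other post-baseline values to condition on. Here it has none. Someone without a 12-week value helps only to estimate the baseline mean, so the arm difference comes in effect from a baseline-adjusted analysis of completers. If people whose pressure has stayed high are likelier to miss the visit, and if the arms lose different numbers, the two sets of completers are not comparable. More loss of poorly controlled participants from the control arm would make the remaining controls look better and shrink the apparent SMS effect.

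BP is a secondary outcome and no decision rule depends on it. However, the aims section presents the pilot as the source of preliminary data for an efficacy trial, so the estimate and its method may be carried forward.

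**Working it through.** **Inputs from the documents.** 24 participants, read as 12 per arm (Sample Size); 30% clinic no-show rate, and BP at enrolment and 12 weeks (Secondary measures of interest); mixed model (Analytical Plan); 2-week nurse BP check (Design). The plan gives no BP effect size, SD, power or allowance for missing data, so there is no figure of its own to reproduce.

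**Assumed inputs.** SD 15 mmHg; correlations 0.6 (weeks 0 and 2), 0.7 (weeks 2 and 12) and 0.5 (weeks 0 and 12); true 12-week difference -6 mmHg; log-odds of a missing 12-week reading rising by 0.8 per SD of BP.

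**1. How many readings could be missing.** 0.30 × 12 = 3.6 per arm and 0.30 × 24 = 7.2 overall. The binomial 5th to 95th percentiles are 4 and 11, and the chance of five or more is 89%. This treats every no-show as having no reading, so it is an upper figure at that rate.

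**2. How many would still have nothing after baseline once the 2-week reading is added.**
- All attend at 2 weeks: 0.
- 70% attend, independently of week 12: 24 × 0.30 × 0.30 = 2.2.
- 65% of the 12-week no-shows also miss week 2 (assumed): 7.2 × 0.65 = 4.7.

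**3. Precision.** With baseline adjustment, SE = SD × √[(1 − ρ²)(1/n₁ + 1/n₂)].
- No missing data, ρ = 0.5: 15 × √(0.75 × 2/12) = 5.30 mmHg.
- 8.4 completers per arm: 15 × √(0.75 × 2/8.4) = 6.34 mmHg.
- The same with a 2-week reading for everyone, all correlations 0.5: 6.23 mmHg.

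The recovered share of lost information is (1/6.23² − 1/6.34²) / (1/5.30² − 1/6.34²), about 8%. With a common correlation of 0.3 or 0.7 it is 4% or 13%. With 70% attendance at week 2 it is 3%, 6% and 9% for correlations 0.3, 0.5 and 0.7. The gain in precision is small.

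**4. Bias towards zero (large-sample simulation, mmHg).** The first three rows assume full 2-week attendance. In the last row, 65% of 12-week no-shows and 15% of attenders miss week 2.

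| Missing at 12 weeks, control v SMS (assumed) | Follows 2-week BP: baseline only → with 2-week reading | Follows unseen 12-week BP: baseline only → with 2-week reading |
|---|---|---|
| 30% v 30% | about 0 → about 0 | about 0 → about 0 |
| 30% v 25% | 0.2 → 0.0 | 0.4 → 0.3 |
| 37% v 15% | 0.9 → 0.0 | 1.7–1.8 → 1.2 |
| 37% v 15%, 2-week visit often missed by the same people | 0.9 → 0.4–0.5 | 1.7–1.8 → 1.4–1.5 |

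With equal missingness and the same mechanism in both arms, the distortions cancel in the difference. The reduction therefore runs from 0 to 0.9 mmHg.

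**5. Bias against noise.** At 37% v 15% the expected completers are 12 × 0.63 = 7.56 and 12 × 0.85 = 10.2, so SE = 15 × √[0.75 × (1/7.56 + 1/10.2)] = 6.2 mmHg. The largest reduction, 0.9, is about one seventh of that (0.9/6.2 = 0.15).

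**The case against.** **The gap between arms is not in the documents.** This stands. A reader might infer that the plan expects the arms to differ in no-shows and that the SMS effect will therefore be understated by 1 to 2 mmHg. The plan gives one clinic rate and compares it with the study participants as a whole; it forecasts no difference between arms. The 37% v 15% rows are one unfavourable scenario.

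**A no-show need not lack the outcome.** This also stands. It is tempting to read the plan as saying that 12-week BP will be missing for every no-show. The definition covers only those not seen within 7 days. They may attend later, staff try to reach them weekly up to three times, and no window bars a late reading. Patients without transport are excluded, so the clinic's 30% may not apply either.

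**The 2-week visit is advised, not assured.** The people who miss week 12 may be those who miss week 2. This weakens the remedy but does not cancel it, as the last table row shows.

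**The text may already allow it.** The outcome section mentions follow-up readings by nurses, and the Analytical Plan takes BP values from the record when they exist. These are general statements. The sentence that defines the outcome data names two time points, and nothing in the plan names a 2-week value.

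**At this sample size it hardly matters.** For the pilot's own estimate this is largely right. The case for the change rests on its low cost and a more plausible missing-data assumption.

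**Conclusion.** The point holds as a cheap improvement to a secondary outcome. With two extracted time points, anyone without a 12-week reading contributes baseline only, and the arm difference depends on missingness being unrelated to post-enrolment BP given arm and baseline. Up to about 7 of 24 could be affected at the 30% rate, fewer if late visits count.

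Adding the 2-week reading reduces bias by about 0 to 0.9 mmHg against an SE near 6 mmHg and recovers roughly 3% to 13% of the lost information. These sizes rest on the assumed SD, correlations, missingness mechanism, gap between arms and 2-week attendance, none of which the documents supply.

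A reader might also infer that the 2-week reading would eliminate the bias. That is so only if missingness depends on the 2-week value and everyone attends then. If it follows the unseen 12-week BP, most of the bias remains.

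**What to change.** In Secondary measures of interest, change the extraction sentence to name SBP and DBP at enrolment, at the 2-week nurse visit and at 12 weeks, and say whether a late reading counts as the 12-week value. In the Analytical Plan, state that the mixed model uses all three visits, includes every randomised participant and reports the 12-week arm difference as the estimate.

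Including everyone requires reconciling the analysis sets in the same section, which are limited to participants who answered an SMS or supplied a BP reading. That is a separate and larger problem, to be settled first.

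The cost is one more routine value to abstract from a record already in use, plus the wording. No extra visit is needed. The 2-week value will itself be missing for some participants.

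Home readings should not be used as a sensitivity analysis for no-shows as the text stands. Design says in one place that every participant receives a monitor and in another mentions only the intervention arm. Unless those statements are reconciled, such an analysis could have data from one arm only.

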Aim 1: Feasibility will be assessed through examination of participant recruitment, retention and engagement. Specifically, we will look at the number of participants who refuse to participate in the pilot at the time of recruitment and the reason they declined participation. Secondary impacts of interest include: medication adherence as measured by the four-item MA Questionnaire (MAQ) and change in systolic and diastolic blood pressure at 3 months.

Aim 2: To test the acceptability of a 3-month SMS-based intervention in adults with uncontrolled hypertension. One cohort of 24 participants will be recruited for the SMS intervention. Acceptability will be assessed using the systems usability scale (a validated questionnaire that measures usability reliably in small samples)¹⁸ and eliciting free comments after the survey.

At the end of this pilot project, we will have preliminary data essential for a future formal efficacy trial, to be proposed in a subsequent application to the AHRQ.

Our **first hypothesis** is that over 50% of contacted patients will respond to SMS messages and over 50% will check HBPM. This estimate is based on previous study by Bobrow and

colleagues in a similar patient population.³ Our **second hypothesis** will be that > 75% will be satisfied with the service (OK or above on the usability survey).⁹

Methods and Measures

Design

A randomized control trial of 24 non-adherent participants will be monitored and followed for 3 months; An ambulatory BP arm device will be provided to all participants with printed instructions in English or Spanish (from the American Heart Association) on how to measure BP at home (HBPM). Patients will be instructed on checking their BP at least twice a week.^{14,19} Text messages will be generated by Twilio platform, keeping a record of participants contacted, sent and received texts. Participants in the control arm will receive standard of care education for controlling high blood pressure in clinic by their healthcare providers. They will be followed to monitor any changes in their BP throughout the duration of the study.

Study team members will identify patients with uncontrolled hypertension during clinic visits. Study team members will approach patients 18 years or older who have uncontrolled HTN (SBP>130 or DBP >80) and have 2 or more BP medication(s) on their medication list.

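### A feasibility conclusion is attached to a secondary measure (no-show below the clinic's own 30%), with no link to the recruitment, retention and engagement outcomes that define feasibility

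*Combined protocol and SAP*

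**What the plan says.** All references are to the combined protocol and SAP.

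- **Specific Aims, Aim 1:** "Feasibility will be assessed through examination of participant recruitment, retention and engagement". The secondary impacts named there are "medication adherence as measured by the four-item MA Questionnaire (MAQ) and change in systolic and diastolic blood pressure at 3 months".
- **Outcome Measure(s), A- Feasibility:** screening, recruitment, retention and engagement are listed. Only engagement has a number: "We will use 44% as our cut off". The plan does not say what follows if it is missed. Retention and recruitment are tracked without thresholds.
- **Specific Aims, first hypothesis:** more than 50% are expected to respond to messages and more than 50% to check home blood pressure.
- **Secondary measures of interest, no-show rate:** "Our current clinic no-show rate is 30" per cent, and "therefore if the study participants no-show rate is less than 30% we will consider our tool a feasible intervention". A no-show is a participant who has not attended within 7 days of the scheduled follow-up appointment.
- **Analytical Plan:** no rule combines or ranks the feasibility criteria. The full analysis set needs at least one SMS reply, and the primary analysis needs at least one blood pressure reading. Neither set is tied to the no-show rate.

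**The concern.** The only sentence that says when the tool will be called feasible sits outside the feasibility section and rests on clinic attendance. Keeping an appointment does not show that a participant answered the messages, sent readings or went on using the system. If attendance is good and engagement is poor, the plan's one explicit rule points to feasible, and no text says that the engagement result should hold that conclusion back.

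The threshold is also weak as a test of the tool. It is the rate the clinic already has, it is applied to an observed proportion with no allowance for sampling error, and it does not use the randomised control arm. The wording does not limit the rule to the SMS arm, so control attendance may count as well. The selection criteria exclude patients who lack transport to visits, which could lower no-shows without any help from the tool.

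At stake is how far the pilot's main conclusion can be relied on. Specific Aims says that the pilot's data will feed a proposal for an efficacy trial.

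**Working it through.** The plan derives no operating characteristics for the no-show rule or for the sample size, so there is no figure of its own to reproduce.

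**Inputs from the document:** no-show threshold below 30%; current clinic rate 30%; engagement cut-off 44%; 24 participants in two groups.

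**Assumptions:** 12 per arm; engagement read as the proportion of the 12 SMS-arm participants who send at least one home reading; the no-show denominator is everyone randomised to the SMS arm (12) or to both arms (24).

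**Step 1. Counts that meet the rule.** 3/12 = 25.0% and 4/12 = 33.3%, so at most 3 of 12. 7/24 = 29.2% and 8/24 = 33.3%, so at most 7 of 24.

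**Step 2. Chance of meeting the rule if attendance is unchanged.** With X ~ Binomial(n, 0.30):

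- n = 12: P(X ≤ 3) = 0.7^12 + 12(0.3)(0.7^11) + 66(0.3^2)(0.7^10) + 220(0.3^3)(0.7^9) = 0.0138 + 0.0712 + 0.1678 + 0.2397 = 0.4925
- n = 24: P(X ≤ 7) = 0.5647

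If the true rate were 40%, worse than the clinic's, the same sums give 0.225 and 0.192.

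**Step 3. Precision at the edge of the rule.** Exact (Clopper-Pearson) 95% intervals are 5.5% to 57.2% for 3/12 and 12.6% to 51.1% for 7/24. Both contain 30%.

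**Step 4. Chance that the two criteria disagree.** Steps 2 and 3 describe the threshold. Disagreement is a separate quantity: the no-show rule is met and engagement misses 44%. Since 5/12 = 41.7% and 6/12 = 50.0%, reaching the cut-off takes at least 6 of 12. The document gives no engagement rate to expect under failure, so a range is assumed, with a true no-show rate of 30% and no-show independent of engagement:

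P(disagree) = P(no-show rule met) × [1 − P(at least 6 of 12 engaged)]

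| Assumed true engagement | P(at least 6 of 12) | Disagree, no-show over 12 | Disagree, no-show over 24 |
|---|---|---|---|
| 20% | 0.019 | 0.48 | 0.55 |
| 25% | 0.054 | 0.47 | 0.53 |
| 30% | 0.118 | 0.43 | 0.50 |
| 44% | 0.445 | 0.27 | 0.31 |
| 50% | 0.613 | 0.19 | 0.22 |

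For example, 0.4925 × (1 − 0.019) = 0.48. If participants who text back also tend to attend, independence fails and disagreement would be less common than shown.

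**Step 5. The two engagement figures.** Under the reading above, 44% needs 6 of 12, while more than 50% needs 7 of 12. They are therefore different criteria at this sample size.

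**The case against.** The strongest reply is that the protocol never says no-show decides alone or overrides anything. It commits to examining every Aim 1 domain, so no-show may have been meant as one criterion among several, and poor texting would be visible in the report. Attendance belongs to the study's rationale, and completed visits are tracked weekly. Aim 1's list of secondary impacts is worded as inclusive, so leaving out attendance there proves little. Nothing makes the later trial formally depend on the word feasible.

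Much of this stands. It rules out reading the sentence as a declared override, and the omission from Aim 1's list should carry no weight. It does not supply the missing link: the sentence is a plain if-then with no precondition, and no section says how the criteria combine.

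Two stronger readings are tempting.

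- *A tool that nobody replies to could be called feasible, whatever the denominator.* The document does not support this. Both sets in the Analytical Plan require a reply or a reading. If either supplied the denominator and nobody replied, there would be no one in whom to calculate a no-show rate.
- *The 0.49 and 0.56 measure the conflict between two routes to feasibility.* They do not. They follow from setting the threshold at the clinic's own rate and judging it on a point estimate, and would be the same if no-show were the sole designated primary criterion.

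**Conclusion.** The point holds as a defect in the decision rule. A secondary measure carries a free-standing feasibility conclusion that is neither conditional on the outcomes defining feasibility nor combined with them. This rests on the text and needs no calculation.

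Two consequences have a size. A tool that leaves no-show at 30% meets the rule with probability 0.49 (12 participants) or 0.56 (24 participants), assuming 12 per arm. The chance that the rule is met while engagement misses 44% runs from 0.19 to 0.55 over assumed engagement rates of 50% down to 20%. That range depends on independence and on a denominator of all randomised participants or all in the SMS arm, which the plan does not state, so it is an illustration only.

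The change should be made: followed literally, the rule can yield an unsound conclusion, and the remedy is cheap.

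**What to change.** 1. In the no-show paragraph, delete the clause that calls the tool feasible when the rate is below 30%.
2. In its place, state that no-show is a secondary outcome, reported by randomised arm among all randomised participants with a 95% confidence interval, and cannot by itself establish feasibility. The Analytical Plan already provides for descriptive statistics by group and intervals for differences, so the additions are the denominator, the interval for each arm and the limit on interpretation.
3. In part A, state that feasibility is concluded from the Aim 1 domains (recruitment, retention and engagement), and say what is required of each and how they combine. Engagement should not become the sole gate, because Aim 1 names three domains.
4. Before doing so, reconcile the 44% cut-off with the over-50% hypothesis, and define the engagement measure and its denominator.

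Items 1 and 2 take a sentence or two. Items 3 and 4 need a decision by the investigators but no extra participants or data. The downside is that one easy route to a positive conclusion is lost.

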recommendations by HTN guidelines, which designate a hypertensive urgency to be 180/110 mm Hg or higher and hypotension 90/60 or lower.²

Patients who no show to the follow up visits will be telephoned to assess adherence barriers. The study team member will create a telephone encounter in the electronic health record to document their discussion and route it to the patient's PCP. Patients who refuse participation in the study will be asked for the reason and their responses will be recorded to determine any barriers to participation. Study team members will attempt to contact patients who miss follow up visits every week up to 3 times, if after the 3rd time the patient is still not able to be reached, the patient will be lost to follow up.

Setting

The study team will recruit patients who fall within the eligibility criteria from Wake Forest Baptist Medical Center.

Subjects selection criteria

Eligibility and recruitment

Inclusion criteria

Patients 18 years and older who have SBP>130 or DBP >80 during an office visit encounter in the past 6 months and have BP medication(s) on their medication list.

- Own a phone with SMS capability
- Non-adherent-MAQ score of 1 to 4
- Vulnerable population (Black, Hispanic or education level < or equal high school (as an indicator of low SES)

Exclusion Criteria

- End-stage renal disease (on hemodialysis or peritoneal dialysis)
- Kidney transplant recipients
- Unable to afford BP medications or lack transportation to clinic visits
- Hospice or nursing home care
- Dementia or cognitive impairment on the problem list

Sample Size

24 patients –We will randomize 12 patients into 2 groups

Interventions and Interactions

Pilot randomized controlled study.

Participants in the SMS intervention arm will receive usual care and SMS texting and phone calls. Study team members will send secure SMS messages to participants weekly for four weeks and then every other week until their next appointment.

The secure messaging system will be as follows

Introductory message:

Welcome to managing your blood pressure with the Nephrology/ Internal medicine clinics at Wake Forest. Try to take your BP meds at the same time every day to keep your BP under control! Make it part of your daily routine:

First week

Adherence checkpoint:

1. *Good morning! Did you take your blood pressure medications today?*

“No” Response:

1. *Let's try to stay on top of taking them daily! You can do this!*

Additional prompts:

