potential subjects during recruitment will be protected by collecting only necessary identifiers and using a private room during the interview process.

Informed Consent

The study team will recruit patients in the renal and internal medicine clinics. Signed informed consent will be obtained from each subject. Participants will be consented in a private room in the clinic. Group assignment will be determined using blocked randomization.

Participants will either receive an educational pamphlet or use their own mobile phone to communicate with the study coordinator via SMS. HIPAA-compliant SMS text messages will be sent to participants through any of the local mobile phone network providers.

Confidentiality and Privacy

Confidentiality will be protected by collecting only information needed to assess study outcomes, minimizing to the fullest extent possible the collection of any information that could directly identify subjects, and maintaining all study information in a secure manner. To help ensure subject privacy and confidentiality, only a unique study identifier will appear on the data collection form. Any collected patient identifying information corresponding to the unique study identifier will be maintained on a linkage file, stored separately from the data. The linkage file will be kept secure, with access limited to designated study personnel. Following data collection subject identifying information will be destroyed after three years using a shredder, consistent with data validation and study design, producing an anonymous analytical data set. Data access will be limited to study staff. Data and records will be kept locked and secured, with any computer data password protected. No reference to any individual participant will appear in reports, presentations, or publications that may arise from the study. To prevent breach of confidentiality on subject's cell phone device the study team will ensure the subject is aware of the configuration feature on the device to only show text messages upon unlocking the phone.

Data and Safety Monitoring

The principal investigator will be responsible for the overall monitoring of the data and safety of study participants. The principal investigator will be assisted by other members of the study staff.

Reporting of Unanticipated Problems, Adverse Events or Deviations

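### The no-show feasibility rule does not say whose rate is compared with 30%, so the same data can pass or fail depending on the arm and denominator chosen

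*Combined protocol and SAP*

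**What the plan says.** Under Secondary measures of interest, the no-show event has a time window: "If participants fail to come to their f/u visits within 7 days of their scheduled follow-up appointment", the participant is a no-show. The benchmark is introduced by "Our current clinic no-show rate is 30" (per cent), and the decision rule follows: "if the study participants no-show rate is less than 30% we will consider our tool a feasible intervention". No arm is named, and no denominator is given.

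The Retention item under Outcome Measure(s), by contrast, does name its arm: "the proportion of participants who continue to use the myHealth tool per month through three months will be tracked for the intervention".

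The Analytical Plan defines a set based on replies: "The full analysis set will include participants who have responded to at least one SMS message post-randomization". It does not say whether the no-show outcome uses that set. For primary and secondary outcomes it also plans that "descriptive statistics and 95% confidence intervals will be used to summarize the differences between groups".

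The Sample Size section gives 24 patients in two groups, read here as 12 per arm. In the Design section, controls receive only standard education and monitoring.

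**The concern.** The rule judges an intervention, yet its literal numerator and denominator include people who were not offered that intervention. Good attendance by controls can carry the tool over the line, and poor attendance by controls can sink it.

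The responder set has a different problem. Controls are not sent the study's messages, so they drop out. So do SMS-arm patients who never replied, who are plausibly the ones least likely to attend. A rate computed in that set would tend to flatter the tool.

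The rule carries an explicit verdict, and the pilot is meant to inform a later efficacy trial. If the denominator is not fixed in advance, it can be chosen after the counts are known.

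**Working it through.** **Inputs.** Threshold: observed rate below 30% (Secondary measures of interest). Size: 12 per arm (Sample Size, read as equal allocation). The documents give no derivation of the 30% or of the sample size, so there is no planned operating characteristic to reproduce. True no-show rates below are assumptions.

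**Step 1: what counts as a pass.**
- SMS arm, n = 12: 3/12 = 25.0% passes and 4/12 = 33.3% fails, so a pass is 3 or fewer.
- Pooled, n = 24: 7/24 = 29.2% passes and 8/24 = 33.3% fails, so a pass is 7 or fewer.

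**Step 2: same data, opposite verdicts.**

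| Data | Reading A | Reading B |
|---|---|---|
| SMS 4/12, control 2/12 | SMS arm 33.3%: fail | pooled 6/24 = 25.0%: pass |
| SMS 3/12, control 5/12 | SMS arm 25.0%: pass | pooled 8/24 = 33.3%: fail |
| SMS 4/12, where two of the four no-shows are the only patients who never replied | all randomised to SMS 33.3%: fail | responders 2/10 = 20.0%: pass |

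**Step 3: how often the SMS-arm and pooled readings disagree.** Let X1 (SMS) and X0 (control) be independent Binomial(12, p) with the same p. Then

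P(disagree) = P(X1 ≤ 3 and X1 + X0 ≥ 8) + P(X1 ≥ 4 and X1 + X0 ≤ 7),

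summed over all 13 × 13 outcomes:

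| Assumed p | SMS passes, pooled fails | SMS fails, pooled passes | Disagree |
|---|---|---|---|
| 0.20 | 0.0235 | 0.1397 | 0.163 |
| 0.30 | 0.0889 | 0.1611 | 0.250 |
| 0.40 | 0.1040 | 0.0706 | 0.175 (0.1746) |

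If the arms differ, the gap can be wider. With SMS at 30% and control at 15% (assumed), the pooled reading passes in 85% of trials and the SMS-arm reading in 49%.

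**Step 4: precision of the SMS-arm reading.** The Clopper-Pearson 95% limits for x of n are the 0.025 quantile of Beta(x, n − x + 1) and the 0.975 quantile of Beta(x + 1, n − x). For 3/12 these are 5.5% and 57.2%. Only 0/12 (0 to 26.5%) has its upper limit below 30%.

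**The case against.** The strongest reply is that the SMS arm is the natural reading, since only that arm uses the tool. That is fair, but the text does not say it. The Retention item does name its arm, and Aim 2 describes a single cohort of 24 recruited for the SMS intervention, so a denominator of 24 is not far-fetched.

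A second reply is that the reply-based analysis set is a wider problem and is not linked to this rule. That also stands in part. It affects every between-group outcome, and exempting one measure does not cure it. But nothing in the plan keeps the no-show outcome out of it.

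A reader might go further in three ways that the documents do not support.

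- *That the rule passes too easily.* At a true rate of 20% in both arms, the SMS-arm rule passes 79% of the time. That is correct behaviour for a rule asking whether the rate is below 30%. In 41% of such trials it passes while the SMS arm has at least as many no-shows as controls, but that figure includes ties: 22% have strictly more and 18% the same number. The rule claims feasibility, not an effect on attendance.
- *That the control arm is ignored.* The Analytical Plan already covers by-group description and between-group intervals for secondary outcomes. Only the wording of the verdict leaves them out.
- *That the 30% is unfounded or biased.* It is labelled as the current clinic rate. Its source, period and clinic are not given, and Informed Consent says that "The study team will recruit patients in the renal and internal medicine clinics". The sample differs from a general clinic population in ways that pull in both directions: recruited at an attended visit, excluded for lack of transportation, selected for non-adherence. No direction of bias can be claimed. This is a minor reporting note.

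**Conclusion.** The point holds for the arm and the denominator. As written, the feasibility verdict is not determined by the data: the SMS-arm and pooled readings disagree in roughly one trial in six to one in four, assuming 12 per arm, independent patients and a common true rate of 20% to 40%. The responder set can reverse the verdict as well. How often it would do so cannot be calculated, because the documents do not give a joint rate of replying and attending.

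The weight is moderate. This is one secondary measure in a 24-patient pilot, and the fault is in specification, not arithmetic. It is still worth correcting, because the literal reading counts people who never receive the tool and the responder reading removes those least engaged with it.

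**What to change.** **Secondary measures of interest.** State that the 30% criterion applies to the SMS arm only, with everyone randomised to that arm as the denominator. State how a participant with no scheduled follow-up visit, or who withdraws, is counted; otherwise two analysts could still differ. Add that a rate below 30% is a descriptive feasibility benchmark, read beside the control-arm rate and the already planned between-group difference with its 95% confidence interval, and is not evidence that the tool changed attendance.

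**Analytical Plan.** Add one sentence: the no-show outcome is analysed in all randomised participants by assigned arm, not in the set defined by text-message replies.

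If convenient, note the clinic and period behind the 30%.

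**Cost.** A few sentences and no new visits. Completed office visits are already tracked, but that count alone does not show attendance within the 7-day window, so the scheduled and attended dates must be recorded in both arms. The criterion will rest on 12 patients, with the wide interval shown above, and will be somewhat harder to meet than among responders. The between-group difference will also be imprecise: 3/12 against 4/12 gives −8 percentage points, with a Newcombe 95% interval of about −40 to +26.
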